## **INTRODUCTION/BACKGROUND**

Psoriasis is a common, chronic inflammatory skin disease that is characterized by the formation of sharply demarcated, scaly, erythematous plaques. It is a prevalent disease, affecting about 2.2% of the population in the United States.[1] Psoriasis has a high impact on patients' quality of life, with many reporting discomfort, itching, and significant social and emotional burden secondary to the disease. [2, 3] Without treatment, remission from psoriasis is unlikely. [4] Traditional treatment options include topical steroids and vitamin D analogues, and systemic immunosuppressive agents such as cyclosporine and methotrexate. However, these treatments are often not as efficacious as would be desirable, and are associated with significant side effects and risks. In the past several years, the development of biologic agents, in particular monoclonal antibodies, has revolutionized the treatment of psoriasis.

Brodalumab is a human interleukin-17 receptor A (IL-17RA) antagonist recently approved for the treatment of moderate-to-severe plaque psoriasis. Clinical trials of brodalumab included 3 multicenter, randomized, double-blind, controlled trials which enrolled a total of 4373 adult subjects with moderate-to-severe plaque psoriasis.[5] At week 12, PASI-75 and PASI-100 responses were seen in about 85% and 40% of patients, respectively. Nearly 80% of patients achieved static Physician's Global Assessment (sPGA) scores of clear (0) or almost clear (1) at week 12. Maintenance of treatment effect was also established, with high response rates seen through week 52. Of note, approximately 30% of patients reported previous treatment with a biologic, and 12% reported treatment failure with a previous biologic. [5] At present, other biologic drugs that target the IL-17 signaling pathway include secukinumab and ixekizumab, although these agents inhibit the IL-17A ligand, rather than its receptor. It is unknown how patients who have failed treatment specifically with other IL-17 targeting agents respond to brodalumab treatment.

This study will evaluate the safety and efficacy of brodalumab in the treatment of moderate-to-severe psoriasis in patients who have previously failed treatment with interleukin (IL)-17A therapies. Failure of IL-17A therapy will be defined as previous treatment with either secukinumab or ixekizumab for at least 3 months without achieving PASI-75 response or a 50% loss of original improvement. Forty patients will be enrolled in this 16-week open-label study. Patients will be enrolled at three to four different sites in the US. After enrollment, study visits will occur at monthly intervals, with patients receiving 210 mg of brodalumab subcutaneous injection at weeks 0, 1, and 2, followed by 210 mg every 2 weeks. At each visit, patients will be evaluated for change in sPGA (Physician's Global Assessment), PASI score, and any signs or symptoms of adverse events. Laboratory screening will include tests for tuberculosis and neutropenia. The primary efficacy endpoint will be the proportion of patients achieving a score of "0-clear" or "1-almost clear" in the sPGA score after 16 weeks of treatment. After completion of the 16-week trial, patients may desire to continue treatment with brodalumab. Efforts will be made to provide drug to these study patients, including those who do not have insurance.

## **HYPOTHESIS:**

### **Primary Hypothesis:**

1. It is hypothesized that treatment with brodalumab, an IL-17RA antagonist, will be effective in the treatment of moderate-to-severe psoriasis patients who have previously failed treatment with IL-17A therapies.

## **OBJECTIVES:**

**Primary objective:** To evaluate the efficacy of brodalumab in the treatment of moderate-to-severe psoriasis patients who have previously failed treatment with IL-17A therapies by measuring different scoring systems for psoriasis (PASI, BSA, sPGA; see appendix) at week 16.

**Secondary objective:** To determine the safety of brodalumab in the treatments of moderate-to-severe psoriasis patients who have previously failed treatment with IL-17A therapies.

## **ENDPOINTS:**

**Primary endpoint:** Proportion of patients achieving a score of “0-clear” or “1-almost clear” in the sPGA score after 16 weeks of treatment.

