### **Inclusion criteria:**

1. Male or female subject at least 18 years of age
2. Subject is able to provide written informed consent and comply with the requirements of this study protocol.
3. Have both a sPGA score of  $\geq 3$  and BSA  $\geq 5\%$  prior to randomization.

4. Subjects who are women of childbearing potential must have a negative urine pregnancy test at screening and must be practicing an adequate, medically acceptable method of birth control for at least 30 days before Day 0 and at least 6 months after the last study drug administration. Acceptable methods of birth control include intrauterine device (IUD); oral, transdermal, implanted or injected hormonal contraceptives (must have been initiated at least 1 month before entering the study); tubal ligation; abstinence and barrier methods with spermicide. Otherwise, if not of childbearing potential, subjects must: have a sterile or vasectomized partner; have had a hysterectomy, a bilateral oophorectomy or be clinically diagnosed infertile; or be in a menopausal state for at least a year.
5. Tuberculin purified protein derivative (PPD) or QuantiFERON TB-Gold test (QFT) negative at the time of screening, or if patient has a history of positive PPD or QuantiFERON, he/she has initiated or completed the appropriate prophylaxis.
6. Subject is judged to be in good general health as determined by the principal investigator based upon the results of medical history and laboratory profile.
7. Subject has previously failed treatment with an IL-17A agent, secukinumab or ixekizumab, (where available, defined as previous treatment with either drug for at least 3 months without achieving PASI-75 response or a 50% loss of original improvement).
8. Last administration of secukinumab or ixekizumab  $\geq$  28 days prior to Baseline.

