#### **STATISTICAL METHODS:**

Individual efficacy variables, the sum of those variables, and safety parameters will be analyzed separately. Subjects who discontinue prematurely because of inadequate response or because of adverse events will have their last results carried forward for purposes of analysis.

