## Appendix C

### Static Physician Global Assessment (sPGA)

sPGA	0	1	2	3	4
Induration (I) Averaged over all lesions	no evidence of plaque elevation	minimal plaque elevation (0.25 mm)	mild plaque elevation (0.5 mm)	moderate plaque elevation (0.75 mm)	severe plaque elevation (> 1 mm)
Erythema (E) Averaged over all lesions	no erythema, hyperpigmentation may be present	faint erythema	light red coloration	moderate red coloration	bright red coloration
Scaling (S) Averaged over all lesions	no evidence of scaling	minimal; occasional fine scale over <5% of lesion	mild; fine scale dominates	moderate; coarse scale predominates	severe; thick scale predominates

Add I + E + S = \_\_\_\_\_ / 3 = \_\_\_\_\_ (Total Average)

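### Does the primary endpoint fail because Appendix C scores the sPGA in thirds and no rule says whether an average of 1.33 is a response?

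*Combined protocol and SAP*

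**What the plan says.** The plan uses the sPGA in five places.

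- **Endpoints.** The primary endpoint is "Proportion of patients achieving a score of" 0 or 1, labelled clear and almost clear, "in the sPGA score after 16 weeks of treatment".
- **Introduction/Background.** The study summary repeats this: "The primary efficacy endpoint will be the proportion of patients achieving a score of" 0 or 1, with the same labels. The review of the earlier brodalumab trials pairs the same two words with the same two whole numbers.
- **Objectives.** The primary objective is to be assessed "by measuring different scoring systems for psoriasis (PASI, BSA, sPGA; see appendix) at week 16", which sends the reader to Appendix C for the scale.
- **Appendix C.** Induration, erythema and scaling are each graded 0 to 4. The form has a blank for their sum and a blank for the sum divided by 3, the "Total Average". It has no overall category labels, cut-off or rounding instruction.
- **Inclusion criterion 3.** "Have both a sPGA score of" at least 3, together with BSA of at least 5%. It does not say whether the average is rounded.

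The Statistical Methods section says "Individual efficacy variables, the sum of those variables, and safety parameters will be analyzed separately" and describes carrying last results forward. It gives no responder derivation.

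**The concern.** The endpoint is written in whole numbers and the instrument returns thirds. Most values the form can return are not whole, and the endpoint names only two whole values. A patient graded 2, 1 and 1 at week 16 has an average of 1.33. That patient is a responder if the average is rounded to the nearest whole score and a non-responder if it must not exceed 1.

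This is the only primary endpoint of an open-label, single-arm trial of 40 patients, and the estimated proportion is its main result. Whoever settles the convention may already have seen the scores, and sites could settle it differently. At stake is the reported primary rate, and whether a reader can be sure the rule was not picked because it looked better.

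**Working it through.** **Inputs.** Three items graded 0 to 4 and average = (I + E + S)/3, from Appendix C. Response categories 0 and 1, from Endpoints. N = 40, from Research Design. The documents state no null rate, target rate, significance level or power, so the plan has no figure of its own to reproduce here.

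**1. Possible scores.** The sum runs from 0 to 12, which gives 13 averages. It is divisible by 3 at 0, 3, 6, 9 and 12, so 5 averages are whole and 13 − 5 = 8 are not.

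**2. Classification.** There are 5 × 5 × 5 = 125 grade combinations.

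| Sum | Average | Combinations | Exactly 0 or 1 | ≤ 1 | Nearest whole | Truncated (< 2) |
|---|---|---|---|---|---|---|
| 0 | 0 | 1 | yes | yes | yes | yes |
| 1 | 0.33 | 3 | no | yes | yes | yes |
| 2 | 0.67 | 6 | no | yes | yes | yes |
| 3 | 1.00 | 10 | yes | yes | yes | yes |
| 4 | 1.33 | 15 | no | no | yes | yes |
| 5 | 1.67 | 18 | no | no | no | yes |
| 6 to 12 | 2 or more | 72 | no | no | no | no |
| Combinations counted as response | | 125 | 11 | 20 | 35 | 53 |

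These counts are not probabilities; they show only where the readings part. The exact reading fails patients at 0.33 and 0.67 while passing those at 1.00, who are worse, so no sensible analyst would use it. Truncation would also admit 1.67, but nothing in the text suggests it. That leaves nearest whole score against ≤ 1, which differ only at a sum of 4 (35 − 20 = 15 combinations). No multiple of one third falls on a half, so rounding has no ties.

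**3. Effect per patient.** 1/40 = 2.5 points. Two, four or six patients at 1.33 would give 5, 10 or 15 points.

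**4. Illustrative total (all assumed).** Take three exchangeable normal grades, rounded and clipped to 0–4, with latent correlation 0.5 to 0.95 and SD 1.0 to 2.0. Set the mean to give a stated proportion with average ≤ 1. The points added by rounding are then:

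- proportion 80%: 4.2 to 9.4
- proportion 40%: 6.2 to 16.1
- any proportion from 20% to 90%: 2.5 to 16.1

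These are not bounds. With correlation 0.99 and SD 2.0, for instance, the 80% case falls to about 2.3.

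The only response data in the documents are for the earlier trials at week 12: "PASI-75 and PASI-100 responses were seen in about 85% and 40% of patients", with nearly 80% clear or almost clear. If PASI-100 stands in for sPGA 0, about 40/80 = half of responders are fully clear. Settings at 80% that put 35% to 45% of patients at a sum of 0 give 5.0 to 8.0 points, or 0.050 × 40 = 2.0 to 0.080 × 40 = 3.2 patients. The 16.1 figure comes from a setting where about 4.6% of patients have a sum of 0, roughly 4.6/40 = 12% of responders, which is unlike those data.

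**5. Against sampling error.** The exact 95% interval is 48.3% to 79.4% for 26/40 (65%) and 53.5% to 83.4% for 28/40 (70%). Moving two patients shifts the estimate by 5 points inside intervals about 30 points wide.

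**6. Can either rule be applied later?** Sum = 3 × average, so sum and average determine each other. The form has a blank for each. Any of the rules above can be applied to the stored value, including a value carried forward.

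**The case for a change.** The strongest case for a change is that an undefined responder rule goes to the heart of a trial whose main result is one proportion. The assessors are unblinded, three to four sites take part, and one sentence would settle the matter. That no formal decision changes is little comfort when the estimate is itself the result. Patients here have failed IL-17A therapy and may respond less often than those in the earlier trials, and the illustrative shift is larger at middling response rates.

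Much of this is fair. The convention is not written down, and the documents do not bound the number of patients at 1.33. The 5-to-8-point range borrows from a different population at week 12 and uses PASI-100 as a proxy.

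Two parts carry less weight. First, the text is not neutral. The endpoint is framed in whole, named categories, and the Appendix C columns are headed 0 to 4. Reporting a category from an average means converting it to a whole grade, which rounding does; no passage mentions a cut-off of ≤ 1. This is inference, but it is the natural one. Second, differing site conventions would do lasting harm only if sites recorded a converted category and discarded the average. The form asks for no such conversion; its last blank is the average.

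**Conclusion.** The observation is correct, but it describes an unwritten scoring convention that an analyst can fill sensibly. Neither rule has been shown to be wrong or better than the other, so there is no error to correct. Rounding to the nearest whole score fits the wording, and the count under ≤ 1 can be given beside it from the same data.

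The document-based size is 2.5 points for each patient at 1.33, with all 40 in the denominator. The total is unknown; 5 to 8 points is an assumption-dependent illustration. No hypothesis test, success threshold or comparison depends on it, and the four secondary endpoints use PASI and BSA and are unaffected.

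Inclusion criterion 3 raises the same question at an average of 2.67 (sum 8). It and the endpoint need to be reconciled to one scoring convention; which convention governs entry is not a matter for this review.

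The conclusion rests on sites keeping the sum or the average as the form provides. If only a converted category were stored, the choice could not be revisited and the point would carry more weight.

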### **Secondary endpoints:**

1. Proportion of patients achieving PASI-100 response after 16 weeks of treatment.
2. The proportion of patients who achieve an improvement of 50% or greater in BSA involvement after 16 weeks of treatment.
3. Proportion of patients achieving PASI-75 response after 16 weeks of treatment.
4. Proportion of patients achieving PASI-90 response after 16 weeks of treatment.

## **RESEARCH DESIGN:**

This is an open-label study of a total of 40 subjects enrolled at 3 to 4 sites, with moderate-to-severe psoriasis who have previously failed treatment with an IL-17A agent. Subjects will receive brodalumab 210 mg via subcutaneous injection at weeks 0, 1, and 2, followed by 210 mg every 2 weeks; total study length is 16 weeks.

## **METHODS:**

Informed consent will be obtained at the study site at the time of the first consultation for participation in this study.

After providing informed consent, subjects will be assessed for study eligibility at the Screening visit (day -28 to day -1). At the Screening visit the following procedures will be performed:

1. Medical history and concomitant as well as prior medications/treatments will be reviewed
2. Skin examination will be performed (including assessment of PASI, sPGA, and BSA)
3. Approximately 14 cc (approximately 3 teaspoons) of blood will be drawn for a complete blood count (including differential) (not required if subject can provide results from a previous test performed within 4 months of screening visit).
4. Approximately 5 cc (approximately 1 teaspoon) of blood will be drawn for a QuantiFERON TB-Gold test (QFT) assay; or subjects will undergo tuberculin purified protein derivative (PPD) testing (not required if subject can provide results of a negative test performed within 8 months of screening visit).
5. Females of child bearing potential will have 5 cc (approximately 1 teaspoon) of urine collected for a pregnancy test. This test must be negative in order to qualify for the study.

Subjects will be deemed eligible as per inclusion/exclusion criteria. Qualified subjects meeting all the inclusion and exclusion criteria will be start treatment at Day 0/Baseline (within 28 days of signing the consent form). Female subjects of child-bearing potential will have 2 teaspoons of urine collected for a pregnancy test prior to treatment. This test must be negative in order to continue to qualify for the study. Assessments at this Day 0/Baseline visit include skin examination with assessment of PASI, sPGA, and BSA scores.

Subjects will receive brodalumab (210 mg) via subcutaneous injection using prefilled syringes at Weeks 0, 1, 2, and every 2 weeks thereafter through and including Week 16. Patients will be taught how to administer the drug subcutaneously by a study investigator or designated research staff member at the Baseline visit. They will be dispensed a one-month supply of medication at baseline and each subsequent visit for self-administration at home.

At Weeks 4, 8, 12 and 16 subjects will return for assessment of concomitant medications and adverse events, and skin assessments including PASI, sPGA, BSA scores, and photography of target lesion(s). In addition, females of child-bearing potential will have 2 teaspoons of urine collected for a pregnancy test at each visit.

## **PATIENT POPULATION:**

Prior to enrollment, all subjects must meet the following inclusion and exclusion criteria:

### **Inclusion criteria:**

1. Male or female subject at least 18 years of age
2. Subject is able to provide written informed consent and comply with the requirements of this study protocol.
3. Have both a sPGA score of  $\geq 3$  and BSA  $\geq 5\%$  prior to randomization.

4. Subjects who are women of childbearing potential must have a negative urine pregnancy test at screening and must be practicing an adequate, medically acceptable method of birth control for at least 30 days before Day 0 and at least 6 months after the last study drug administration. Acceptable methods of birth control include intrauterine device (IUD); oral, transdermal, implanted or injected hormonal contraceptives (must have been initiated at least 1 month before entering the study); tubal ligation; abstinence and barrier methods with spermicide. Otherwise, if not of childbearing potential, subjects must: have a sterile or vasectomized partner; have had a hysterectomy, a bilateral oophorectomy or be clinically diagnosed infertile; or be in a menopausal state for at least a year.
5. Tuberculin purified protein derivative (PPD) or QuantiFERON TB-Gold test (QFT) negative at the time of screening, or if patient has a history of positive PPD or QuantiFERON, he/she has initiated or completed the appropriate prophylaxis.
6. Subject is judged to be in good general health as determined by the principal investigator based upon the results of medical history and laboratory profile.
7. Subject has previously failed treatment with an IL-17A agent, secukinumab or ixekizumab, (where available, defined as previous treatment with either drug for at least 3 months without achieving PASI-75 response or a 50% loss of original improvement).
8. Last administration of secukinumab or ixekizumab  $\geq$  28 days prior to Baseline.

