12. History of Crohn's disease.
13. Had a serious infection, been hospitalized, or received IV antibiotics for an infection, within 12 weeks prior to Baseline (Visit 2).
14. Known immunodeficiency, or history of infection typical of an immunocompromised host.
15. At screening, have a neutrophil count <1500 cells/uL.
16. At screening, have a lymphocyte count <800 cells/uL.
17. At screening, have a platelet count <100,000 cells/uL.
18. At screening, have a total white blood count (WBC) < 3000 cells/uL.
19. At screening, have a hemoglobin <8.5 g/dL.
20. Have donated >450 mL of blood within 4 weeks prior to screening (Visit 1), or intend to donate blood during the course of the study.
21. Women who are lactating or breastfeeding.
22. Any other condition that precludes the patient from following and completing the protocol, in the opinion of the investigator.

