## **SAFETY MONITORING**

The study will be conducted in accordance with our department's Standard Operating Procedures, which are based on US FDA Title 21 Code of Federal Regulations and ICH Good Clinical Practice guidelines.

An investigator will review all laboratory results and assess for adverse events. The principal investigator will be informed of all adverse events. In the event that a subject's safety is compromised, the investigator will discontinue the subject immediately.

A DSMB will be formed and will be comprised of two board certified dermatologists experienced in prescribing biologic treatments. All SAEs will be reported to the DSMB board within 24 hours of our being informed of the event. In addition, the DSMB will receive a compiled list of all related adverse events, from all sites, every three months, so that they can determine if the risks have changed and whether or not the study should continue as planned.

**Definition of an AE:** Any untoward medical occurrence in a subject administered a pharmaceutical product that does not necessarily have a causal relationship with the treatment. An AE can therefore be any unfavorable and unintended sign (including an abnormal laboratory finding), symptom, or disease temporally associated with the use of a medicinal (investigational) product, whether or not considered related to the investigational medicinal product.

Investigational Medicinal Product (IMP) includes the drug under evaluation and the comparator drug(s) if specified as part of the research objective, given at any time during the study. Medical conditions/diseases present before starting the drug of interest are only considered adverse events if they worsen after starting the drug of interest.

The occurrence of adverse events will be sought by non-directive questioning of the patient at each visit during the study. Adverse events also may be detected when they are volunteered by the patient during or between visits or through physical examination, laboratory test, or other assessments. All adverse events will be recorded in the study database including the following information:

1. the severity grade (mild, moderate, severe)
2. its relationship to the drug(s) of interest (suspected/not suspected)
3. its duration (start and end dates or if continuing at final exam)
4. whether it constitutes a serious adverse event (SAE)

A SAE is any untoward medical occurrence that at any dose:

- results in death,
- is life-threatening,

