- requires inpatient hospitalization or prolongation of existing hospitalization,
- results in persistent or significant disability/incapacity,
- is a congenital anomaly/birth defect,
- is otherwise a significant medical event.

This includes any SAEs likely to arise from the trial indication or progression of underlying/concomitant illness (es) (e.g. progression of cancer in oncology trials), unless specified in the protocol as study specific exemptions.

Any SAE, irrespective of causality, occurring after the subject has provided informed consent and until four weeks after the subject has stopped study participation must be reported unless otherwise stated in the protocol. SAEs occurring after four weeks from ending study participation should only be reported if considered by the Investigator

attributable to the exposure to the investigational drug(s) during the trial period. This includes the period in which the study protocol interferes with the standard medical treatment given to a subject, even if study treatment has not yet started (e.g. withdrawal of previous treatment during washout period, change in treatment to a fixed dose of concomitant medication).

**Timelines:** All serious adverse events (SAEs) from interventional clinical trials must be reported by the sites to the Lead PI within 24 hours of occurrence of the SAE and to the site's own IRB as required. The Lead PI will then report to the manufacturer and any other authorities.

**Follow-up reports:** All related SAEs will be followed until resolution or until it is judged to be permanent, and an assessment will be made at each visit (or more frequently, if necessary) of any changes in severity, the suspected relationship to the drug of interest, the interventions required to treat it, and the outcome.

**Pregnancies:** Any occurrences of a pregnancy in a patient (or a patient's partner) during study participation will be collected. All pregnancies will be followed up to determine outcome, including spontaneous or voluntary termination, details of the birth, and the presence or absence of any birth defects, congenital abnormalities, or maternal and/or newborn complications.

Should a temporary or permanent suspension occur, we would report the occurrence to all appropriate authorities.

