## Appendix A

### Schedule of Events

	Screening	Baseline/Randomization	Treatment Phase			
	V1	V2	V3	V4	V5	V6/ET
Visit number	V1	V2	V3	V4	V5	V6/ET
Weeks since randomization	-4	0	w4	w8	w12	w16
Informed Consent	x					
Patient-Prescriber Agreement Form		x				
Medical History	x					
Demographics	x					
Inclusion/Exclusion	x	x				
Concomitant Medications	x	x	x	x	x	x
Adverse Events		x	x	x	x	x
Administer IP		x	x	x	x	
Dispense IP		x	x	x	x	
Clinical Efficacy						
sPGA	x	x	x	x	x	x
PASI	x	x	x	x	x	x
BSA	x	x	x	x	x	x
Photographs of target lesion(s) 		x	x	x	x	x
Laboratory Tests						
Quantiferon Gold/PPD (if not done in past 8 months)	x					
Urine Pregnancy (Females of child bearing potential)	x	x	x	x	x	x
Complete Blood Count w/ differential (if not performed in past 4 months)	x					

1 – **Photographs of at least one target lesion should be taken at baseline and then again at every visit thereafter.**  

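### Inclusion criterion 4 can be read as classing a fertile woman with a sterile or vasectomized partner as not of childbearing potential, so that no scheduled pregnancy test, including the pre-dose test, is required for her

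*Combined protocol and SAP*

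**What the plan says.** Inclusion criterion 4 divides women into two groups. Women of childbearing potential need a negative urine pregnancy test at screening and acceptable contraception from at least 30 days before Day 0 until at least 6 months after the last dose. The methods named include an IUD, hormonal contraceptives and "tubal ligation; abstinence and barrier methods with spermicide".

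The criterion then turns to everyone else: "Otherwise, if not of childbearing potential, subjects must: have a sterile or vasectomized partner". The remaining alternatives in that sentence are removal of the uterus or both ovaries, a clinical diagnosis of infertility, or at least a year of menopause. Neither this criterion nor any other section defines childbearing potential separately.

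Testing depends on the same term throughout:

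- Methods, screening visit: a urine test for females of childbearing potential, which must be negative to qualify.
- Methods, Day 0/Baseline: "Female subjects of child-bearing potential will have 2 teaspoons of urine collected for a pregnancy test prior to treatment". This must also be negative.
- Methods, weeks 4, 8, 12 and 16: "females of child-bearing potential will have 2 teaspoons of urine collected for a pregnancy test at each visit".
- Appendix A, Schedule of Events: the row "Urine Pregnancy (Females of child bearing potential" is marked at V1 to V6/ET.

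The exclusion criteria name "Women who are lactating or breastfeeding" but do not name pregnancy.

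**The concern.** Every other item in the second sentence describes the woman's own reproductive status. The partner item describes someone else's. A fertile woman whose partner has had a vasectomy can still become pregnant, through failure of the procedure or through another partner. If the list is read as defining the group, she is classed with women who cannot conceive and drops out of every scheduled test. The stated 30-day and 6-month contraception periods no longer apply to her either.

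The negative test before the first dose is the only explicit entry safeguard against dosing a pregnant woman. The safeguards after entry do not include a scheduled test for her. The Early Termination section requires discontinuation if a subject becomes pregnant, and Safety Monitoring states "Any occurrences of a pregnancy in a patient (or a patient's partner) during study participation will be collected". Both act on a pregnancy once it is known. Detection would rest mainly on what she reports or what examination shows: "The occurrence of adverse events will be sought by non-directive questioning of the patient at each visit during the study". It would therefore be later and less reliable, though not absent.

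**Working it through.** The plan gives no figure to reproduce on this point. The check compares the two readings of criterion 4 and then counts tests and doses.

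**The two readings**

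- *Reading A:* the list defines who is not of childbearing potential. A fertile woman with a sterile or vasectomized partner is then in that group.
- *Reading B:* the term has its ordinary meaning, and the list applies only to women already in that group. She is fertile, so she stays in the tested group.

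On reading B the partner item has no function, because a woman who cannot conceive has no need of a sterile partner. It does some work only if it brings an otherwise fertile woman into the second group. Reading A is therefore at least as natural as reading B.

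**Scheduled tests per woman (Appendix A)**

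V1, V2, V3, V4, V5 and V6 give 6 tests, all conditional on childbearing potential.

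| | Tests required | Tests lost |
|---|---|---|
| Reading A | 0 | 6 − 0 = 6 |
| Reading B | 6 | 6 − 6 = 0 |

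**Doses between consecutive tests**

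The inputs are the dosing weeks in Methods (0, 1, 2, then every 2 weeks) and the visit weeks in Appendix A. I assume that each visit's test comes before that day's dose; the protocol says so explicitly for Day 0.

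| Interval | Dosing weeks | Doses |
|---|---|---|
| V2 to V3 | 0, 1, 2 | 3 |
| V3 to V4 | 4, 6 | 2 |
| V4 to V5 | 8, 10 | 2 |
| V5 to V6 | 12, 14 | 2 |

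The total is 3 + 2 + 2 + 2 = 9. Appendix A shows no administration at V6, which agrees with 9. Methods runs dosing through week 16 inclusive, which gives 9 + 1 = 10.

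The most doses given without an intervening scheduled test is therefore 3 for a tested woman, and 9 or 10 for the woman in question on reading A.

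**Consistency within the criterion**

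Tubal ligation and the IUD are listed as birth control methods, so women relying on either remain of childbearing potential and are tested at every visit. On reading A, a woman with no contraception of her own, who relies on her partner's procedure, is tested at none.

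**The case against.** The strongest reply is that the sentence is conditional. Taken literally, status is settled first and the list is then required of women already in the second group. A fertile woman fails the condition, stays in the first group and is tested. Context points the same way: a protocol that tests women with a tubal ligation is unlikely to mean to exempt fertile women because of a partner. On this view the clause is simply misplaced, and a sensible site would test her.

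That may well be the intent, and some sites may act on it. But the literal reading leaves the partner item without a purpose, and three to four sites could resolve the ambiguity differently.

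Other safeguards can be cited. Medical history is reviewed at screening. Exclusion 22 covers any condition that would prevent completion of the protocol, and a known pregnancy would fall under it. The early-termination visit lists a pregnancy test with no restriction to childbearing potential. The first two help only if the pregnancy is recognised. The last is optional, comes after dosing and applies only to subjects who discontinue. None replaces the pre-dose test.

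The objection is right about scale. The counts describe one hypothetical woman on one of two readings. Enrolment is 40 in total, the number of such women is unknown, and the adverse-event summary gives no embryo-fetal risk from which to size the harm. The endpoints and their analysis are unaffected. The list of birth control methods is also not stated to be exhaustive, so on reading B a partner's vasectomy might already be accepted as a method.

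**Conclusion.** The concern holds. Criterion 4 places a fertile woman beside women who cannot conceive, and no other text corrects this. On reading A, 6 of her 6 scheduled tests are not required, and 9 or 10 doses can be given over 16 weeks with no scheduled test. On reading B nothing is lost. The dose comparison assumes that the test precedes the dose at each visit.

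No trial-level total can be given, since the number of such women may be zero and each one's risk is low. The point should be corrected because the unclear rule governs a pre-dose safety check and the correction is small. Confidence is medium, because the consequence depends on which reading a site adopts.

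**What to change.** Define childbearing potential by the subject's own reproductive status. A woman is not of childbearing potential if she has had a hysterectomy or bilateral oophorectomy, has a clinical diagnosis of infertility, or has been menopausal for at least a year. All other women are of childbearing potential. Move the sterile or vasectomized partner into the list of acceptable birth control methods, next to tubal ligation. The tests already in Methods and Appendix A, and the 30-day and 6-month contraception periods, then apply to these women with no other change.

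The cost is a one-sentence amendment and up to six urine tests for each such woman. A few women could become ineligible: one who tests positive, or one without 30 days of an acceptable method before Day 0, for example because her partner's vasectomy is recent and she uses no other method. Endpoints, sample size and visit schedule do not change.
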